3.10.4. Guidelines for Diarrhea

Episodes of diarrhea have occurred in subjects receiving trametinib (see the Investigator Brochures [Novartis, 2016] for more information). Other, frequent causes for diarrhea including concomitant medications (e.g., stool softeners, laxatives, antacids, etc.), infections by *C. difficile* or other pathogens, partial bowel obstruction, etc., should be clinically excluded.

Guidelines regarding management and dose reduction for diarrhea considered to be related to trametinib by the investigator are provided (see Table 12).

CONFIDENTIAL

Table 12 Management and Dose Modification Guidelines for Diarrhea

CTCAE Grade	Adverse Event Management	Action and Dose Modification
Uncomplicated Diarrhea ^a Grade 1 or 2	
 • Diet: stop all lactose containing products; eat small meals, BRAT-diet (banana, rice, apples, toast) recommended • Hydration: 8-10 large glasses of clear liquids per day (e.g., Gatorade or broth) • Loperamide: initially 4 mg, followed by 2 mg every four hours or after every unformed stool; maximum 16 mg/day. Continue until diarrhea free for 12 hours • Diarrhea > 24h: loperamide 2 mg every two hours; maximum 16 mg/day. Consider adding oral antibiotics • Diarrhea > 48h: loperamide 2 mg every two hours; maximum 16 mg/day. Add budesonide or other second-line therapies (otretotide, or tincture of opium) and oral antibiotics 	
 • Continue trametinib • If diarrhea is grade 2 for > 48h, interrupt trametinib until diarrhea resolves to grade ≤1 • Restart trametinib at the same dose level^d
Uncomplicated Diarrhea ^a Grade 3 or 4 Any Complicated Diarrhea ^b	
 • Clinical evaluation mandatory • Loperamide: initially 4 mg, followed by 2 mg every four hours or after every unformed stool; maximum 16 mg/day. Continue until diarrhea free for 12 hours • Oral antibiotics and second-line therapies if clinically indicated • Hydration: intravenous fluids if clinically indicated • Antibiotics (oral or intravenous) if clinically indicated • Intervention should be continued until the subject is diarrhea free for ≥ 24 hours • Intervention may require hospitalization for subjects at risk of life-threatening complications 	
 • Interrupt trametinib until diarrhea resolves to grade ≤1 • Restart with trametinib reduced by one dose level^{d,e} • If 3 dose reductions of study treatment are clinically indicated, permanently discontinue trametinib

Abbreviation: CTCAE = Common Terminology Criteria for Adverse Events

- Uncomplicated diarrhea** defined by the absence of symptoms such as, cramping, nausea/vomiting ≥grade 2, decreased performance status, pyrexia, sepsis, neutropenia grade ≥3, frank bleeding, and/or dehydration requiring intravenous fluid substitution
- Complicated diarrhea** defined by the presence of symptoms such as, cramping, nausea/vomiting ≥grade 2, decreased performance status, pyrexia, sepsis, neutropenia grade ≥3, frank bleeding, and/or dehydration requiring intravenous fluid substitution
- Loperamide should be made available prior to start of study treatment so loperamide administration can begin at the first signs of diarrhea
- If dose is delayed more than 21 days, discussion with the medical monitor is required to resume therapy.
- Escalation of trametinib to previous dose level is allowed after consultation with the medical monitor and in the absence of another episode of complicated or severe diarrhea in the 4 weeks subsequent to dose reduction.

CONFIDENTIAL

4. INVESTIGATIONAL PRODUCT(S)

The term 'study treatment' is used throughout the protocol to describe any combination of investigational product(s) (IP) received by the subject as per the protocol design. Study treatment may therefore refer to the individual study treatment or the combination of those study treatments.

4.1. Description of Investigational Product(s) and/or Comparators/Placebo

4.1.1. Trametinib

Trametinib will be provided as 0.5 mg and 2.0 mg tablets. Each tablet will contain 0.5 mg or 2.0 mg of trametinib parent (present as the DMSO solvate).

Trametinib commercial available supply with auxiliary label will also be provided by Novartis. The study drug should be administered and stored according to the instructions specified on the drug labels (refer to label, PI, and IB for detailed information).

Trametinib will be shipped to sites by the Clinical Research Management Group. The contents of the label will be in accordance with all applicable regulatory requirements.

4.2. Preparation/Handling/Storage of Trametinib

Handling

Under normal conditions of handling and administration, investigational products (IPs) are not expected to pose significant safety risks to site staff. A Material Safety Data Sheet (MSDS) describing the occupational hazards and recommended handling precautions will be provided to site staff if required by local laws or will otherwise be available from Novartis upon request.

In the case of unintentional occupational exposure notify the study monitor, the Medical Monitor and/or the study manager.

Storage

Study treatments must be stored in a secure area under the appropriate physical conditions for the product. Access to and administration of the study treatments will be limited to the investigator and authorized site staff. Study treatments must be dispensed or administered only to subjects enrolled in the study and in accordance with the protocol. Study medication is to be refrigerated and stored at the temperature specified on the label. Maintenance of a temperature log (manual or automated) is required.

4.3. Product Accountability

In accordance with local regulatory requirements, the investigator, designated site staff, or head of the medical institution (where applicable) must document the amount of study treatments dispensed and/or administered to study subjects, the amount returned by study

CONFIDENTIAL

subjects, and the amount received from and returned to Novartis, when applicable. Product accountability records must be maintained throughout the course of the study. See Appendix 8 for medication diary.

4.4. Treatment Compliance

Treatment compliance will be assessed through querying the subject during the site visits and documented in the source documents, electronic case report form (eCRF), and the medication diary. A record of the number of trametinib tablets capsules dispensed to and taken by each subject must be maintained and reconciled with study treatment and compliance records. Treatment start and stop dates, including dates for treatment delays and/or dose reductions will also be recorded in the eCRF. Investigators must make every effort to bring non-compliant subjects into compliance.

4.5. Treatment of Investigational Product Overdose

In the event of an overdose defined as administration of more than 3.0 mg once daily for trametinib (the maximum tolerated dose defined in the MEK111054 Study), the investigator should:

- contact the Medical Monitor immediately
- closely monitor the subject for adverse events (AEs)/serious adverse events (SAEs) and laboratory abnormalities
- obtain a plasma sample for pharmacokinetic (PK) analysis if requested by the Medical Monitor (determined on a case-by-case basis)
- document the quantity of the excess dose as well as the duration of the overdosing in the electronic case report form (eCRF).

Decisions regarding dose interruptions or modifications will be made by the investigator in consultation with the Medical Monitor based on the clinical evaluation of the subject.

5. STUDY POPULATION

5.1. Number of Subjects

The number of subjects enrolled will be dependent on the early response rate. In stage I, 15 subjects will be enrolled in cohort A and if less than one response is confirmed, the trial will be terminated. If one or more responses are observed, an additional 10 subjects will be enrolled. For cohort B, we will enroll patients concurrently. In stage I we will enroll up to 15 patients. If no responses are seen, this arm will be terminated. If one or more responses occur, we will accrue up to 10 additional patients. However, this exploratory study arm will close at the completion of cohort A accrual.

CONFIDENTIAL

5.2. Subject Selection Criteria

5.2.1. Inclusion Criteria

Specific information regarding warnings, precautions, contraindications, adverse events (AEs), and other pertinent information on the study treatments that may impact subject eligibility is provided in the Investigator Brochures and Supplements [Novartis, 2016].

Deviations from inclusion criteria are not allowed because they can potentially jeopardize the scientific integrity of the study, regulatory acceptability or subject safety. Therefore, adherence to the criteria as specified in the protocol is essential.

Subjects eligible for enrolment in the study must meet **all** of the following criteria:

1. ≥18 years old.
2. Signed written informed consent.
3. Histologically or cytologically confirmed diagnosis of melanoma.
4. BRAF mutation in loci other than V600 (BRAF nonV600 MUT) or BRAF fusion detected by genetic testing of the primary tumor or regional/distant metastasis.
5. Subjects must provide either a fresh or archived tumor sample for correlative study analyses.
6. For subjects with melanoma, archived or freshly biopsied tumor tissue (preferred) must be obtained prior to enrollment. Tissue shipment tracking information should be provided before administration of study treatment is initiated. However, if shipping will be delayed and tissue shipment tracking information is unavailable, study drug may be administered prior to tissue receipt pending discussion with principal investigator.
7. Measurable disease (i.e., present with at least one measurable lesion per RECIST, version 1.1 (Eisenhauer 2009)).
8. All prior anti-cancer treatment-related toxicities (except alopecia and laboratory values as listed on Table 12) must be ≤ grade 1 according to the Common Terminology Criteria for Adverse Events version 4 (CTCAE version 4.0; CTCAE, 2009) at the time of randomization. Subjects with endocrinopathies (e.g. hypopituitarism, hypothyroidism, hypoadrenalism) caused by immune therapies currently on adequate hormone replacement WILL be permitted.
9. Able to swallow and retain oral medication and must not have any clinically significant gastrointestinal abnormalities that may alter absorption such as malabsorption syndrome or major resection of the stomach or bowels.
10. Women of childbearing potential must have a negative serum pregnancy test within 14 days prior to randomization and agree to use effective contraception as defined (see Section 7.3.9).
11. Men with a female partner of childbearing potential must have either had a prior vasectomy or agree to use effective contraception as described in Section 11.1.2.
12. An Eastern Cooperative Oncology Group (ECOG) performance status of 0 or 1. Refer to Appendix for details.

CONFIDENTIAL

13. Adequate baseline organ function as defined in Table 13.

CONFIDENTIAL

Table 13 Definitions for Adequate Baseline Organ Function

System	Laboratory Values
Hematologic	
ANC	≥ 1.0 × 10 ⁹ /L
Hemoglobin	≥ 9 g/dL
Platelet count	≥ 75 × 10 ⁹ /L
PT/INR ^a and PTT	≤ 1.3 x ULN
Hepatic	
Albumin	≥ 2.5 g/dL
Total bilirubin	≤ 1.5 x ULN
ALT	≤ 2.5 x ULN
Renal	
Creatinine or	≤ 1.5 ULN
Calculated creatinine clearance ^b	≥50 mL/min
Cardiac	
Left Ventricular Ejection fraction (LVEF)	≥ LLN by ECHO, >50% if not specified

Abbreviations: ALT = alanine transaminase; ANC = absolute neutrophil count; INR = international normalized ratio; LLN = lower limit of normal; PT = prothrombin time; PTT = partial thromboplastin time; ULN = upper limit of normal.

- a. Subjects receiving anticoagulation treatment may be allowed to participate with INR established within the therapeutic range prior to randomization. PT and PTT > 1.3 x ULN are permitted in these subjects.
- b. Calculate creatinine clearance using standard Cockcroft-Gault formula (Appendix). Creatinine clearance must be ≥50 mL/min to be eligible.

5.2.2. Exclusion Criteria

Deviations from exclusion criteria are not allowed because they can potentially jeopardize the scientific integrity of the study, regulatory acceptability or subject safety. Therefore, adherence to the criteria as specified in the protocol is essential.

Subjects meeting any of the following criteria must not be enrolled in the study:

1. No prior therapy with inhibitors affecting the MAPK pathways at any level (BRAF, MEK, NRAS, ERK inhibitors) for unresectable stage IIIC of Stage IV (metastatic) melanoma. No limit to other therapies (immunotherapy or chemotherapy). Prior systemic treatment in the adjuvant setting is allowed. (Note: Ipilimumab treatment must end at least 8 weeks prior to Study Day 1).
2. BRAFV600 mutation positive.
3. NRAS codon 12, 13, or 61 mutation.
4. Any major surgery, extensive radiotherapy, chemotherapy with delayed toxicity, biologic therapy, or immunotherapy within 21 days prior to Study Day 1, or daily or weekly chemotherapy without the potential for delayed toxicity within 14 days prior to Study Day 1.
5. Taken an investigational drug within 28 days or 5 half-lives (minimum 14 days), whichever is shorter, prior to Study Day 1.
6. Current use of a prohibited medication as described (see Section 10).

CONFIDENTIAL

7. History of another malignancy

Exception: Subjects who have been disease-free for 3 years, or subjects with a history of completely resected, non-melanoma skin cancer, or subjects with indolent second malignancies are eligible. T1a melanoma and melanoma in situ are permitted. Consult Medical Monitor if unsure whether second malignancies meet requirements specified above.

8. Any serious or unstable pre-existing medical conditions (aside from malignancy exceptions specified above), psychiatric disorders, or other conditions that could interfere with the subject's safety, obtaining informed consent, or compliance with study procedures.
9. Known Human Immunodeficiency Virus (HIV), Hepatitis B Virus (HBV), or Hepatitis C Virus (HCV) infection (subjects with laboratory evidence of cleared HBV and HCV infection will be permitted).
10. History of leptomeningeal disease or spinal cord compression secondary to metastasis.
11. Brain metastasis, unless previously treated with surgery or stereotactic radiosurgery and the disease has been confirmed stable (i.e., no increase in lesion size) for at least 6 weeks with two consecutive MRI scans using contrast prior to Study Day 1 (the first MRI may be prior to surgical resection or radiation).
12. A history or evidence of cardiovascular risk including any of the following:
 - a. A QT interval corrected for heart rate using the Bazett's formula (QTc; Appendix 6) ≥ 480 msec;
 - b. A history or evidence of current clinically significant uncontrolled arrhythmias;
Exception: Subjects with atrial fibrillation controlled for > 30 days prior to Study Day 1;
 - c. History of acute coronary syndromes (including myocardial infarction and unstable angina), coronary angioplasty, or stenting within 6 months prior to Study Day 1;

CONFIDENTIAL

- d. A history or evidence of current Class I congestive heart failure as defined by the New York Heart Association (NYHA) guidelines (Appendix 2);
 - e. Treatment refractory hypertension defined as a blood pressure of systolic > 140 mmHg and/or diastolic > 90 mm Hg which cannot be controlled by anti-hypertensive therapy;
 - f. Patients with intra-cardiac defibrillators or permanent pacemakers;
 - g. Known cardiac metastases;
- 13. A history or current evidence of RVO including:
 - a. History of RVO or
 - b. Visible retinal pathology as assessed by ophthalmic examination that is considered a risk factor for RVO such as:
 - Evidence of new optic disc cupping;
 - Evidence of new visual field defects;
 - Intraocular pressure >21 mmHg as measured by tonography.
- 14. Known immediate or delayed hypersensitivity reaction or idiosyncrasy to drugs chemically related to the study treatments, their excipients, and/or dimethyl sulfoxide (DMSO).
- 15. History of interstitial lung disease or pneumonitis.
- 16. Females who are pregnant or nursing (see Section 11.2).

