2. OBJECTIVES AND ENDPOINTS

Table 1 lists the objectives and corresponding endpoints.

Table 1 Objectives and Endpoints

	Objectives	Endpoints
Primary	1. To determine the clinical efficacy of trametinib in advanced BRAF nonV600 ^{MUT} melanoma (“high activity” group)	1. Overall response rate (primary statistical endpoint), duration of response, clinical benefit (CR+PR+SD) per RECIST v. 1.1.
Secondary	1. To characterize the safety of trametinib 2. To evaluate the	1. Safety and tolerability as measured by clinical assessments including vital signs and physical examinations, 12-lead

CONFIDENTIAL

[figure not shown]
	time to progression (TTP) and overall survival (OS) of trametinib in advanced BRAF nonV600 ^{MUT} melanoma	electrocardiograms (ECG), echocardiogram (ECHO) or Multi Gated Acquisition (MUGA) scans, chemistry and hematology laboratory values, and adverse events (AEs). 2. TTP and overall survival.
Exploratory	1. To determine the clinical efficacy of trametinib in advanced BRAF nonV600 ^{MUT} melanoma (“low activity/unknown” group) 2. Identify mechanisms of resistance to trametinib in this patient population	1. Overall response rate, duration of response, clinical benefit (CR+PR+SD) per RECIST v. 1.1. 2. Assess molecular characteristics of patient samples, including archival samples, pre-treatment, early while on treatment, and/or at the time of progression

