3.1. Discussion of Study Design and Study Schematic

This is a Phase II, open-label, multi-center study in subjects with advanced BRAFnonV600^{MUT} melanoma stratified by activity of genetic alterations. Cohort A will be patients with “high activity” BRAF mutations or BRAF fusion events (see appendix A); cohort B is an exploratory group with BRAF mutations of “low activity/unknown” significance. The study is designed to evaluate the response rate to trametinib at the dose approved by the Food and Drug Administration (FDA) for BRAF V600^{MUT} melanoma in the BRAFnonV600^{MUT} population. Safety will also be assessed.

Figure 1: Study Schematic

CONFIDENTIAL

Protocol waivers or exemptions are not allowed. Therefore, adherence to the study design requirements, including those specified in the Time and Events Table (see Section 7.1), are essential.

Enrollment Procedures

All patients **MUST** be registered with the Vanderbilt-Ingram Cancer Center (VICC) Multi-Institutional Coordinating Office prior to the start of protocol treatment. Each participating site must also be registered with their own institution according to their institutional guidelines prior to start of protocol treatment. Prior to the first patient registration, a copy of IRB approval at the respective sites will be requested and on file at the VICC Coordinating Center.

Patients will be centrally registered by sending the completed enrollment packet to the VICC Multi-Institutional Coordinating Office as outlined in the instructions provided on the enrollment form. The enrollment packet must include the following documents:

- Copy of the patient's signed and dated Informed Consent
- Eligibility Checklist
- Coordinating Center enrollment form

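### Exclusion 1 is worded the wrong way round, and no inclusion criterion requires the advanced disease that the objective names

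*Combined protocol and SAP*

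**What the plan says.** The exclusion list in Section 5.2.2 opens with "Subjects meeting any of the following criteria must not be enrolled in the study". Item 1 then begins "No prior therapy with inhibitors affecting the MAPK pathways at any level" and, after naming the inhibitor classes, limits itself to treatment given "for unresectable stage IIIC of Stage IV (metastatic) melanoma". It goes on to permit other therapies without limit and to allow earlier systemic treatment in the adjuvant setting.

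The inclusion list in Section 5.2.1 describes the disease in three items. Item 3 is "Histologically or cytologically confirmed diagnosis of melanoma". Item 4 asks for a non-V600 BRAF mutation or a BRAF fusion "detected by genetic testing of the primary tumor or regional/distant metastasis". Item 7 asks for at least one RECIST-measurable lesion. None of these, and none of the other ten items, sets a stage or a resectability requirement.

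The primary objective in Table 1 (Section 2) is "To determine the clinical efficacy of trametinib in advanced BRAF" non-V600 mutant melanoma, and Section 3.1 also describes the subjects as having advanced disease.

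The lists are to be applied as written. Section 5.2.2 states "Deviations from exclusion criteria are not allowed because they can potentially jeopardize the scientific integrity of the study", Section 5.2.1 says the same of the inclusion criteria, and Section 3.1 adds "Protocol waivers or exemptions are not allowed". Section 3.1 also requires an eligibility checklist in the packet sent for central registration.

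**The concern.** There are two separate faults. First, an inclusion-style sentence sits in the exclusion list, so the main treatment-history criterion says the reverse of what it evidently means. Second, the restriction to advanced disease appears in the objective and the design description but not among the rules that decide who is enrolled.

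At stake is what the cohort A response rate describes. If it mixed patients previously treated with a MAPK inhibitor, or patients with resectable disease, with the intended population, the comparison of 5% with 25% would no longer refer to the population named in the objective. Progression-free and overall survival would also be harder to read, because the background benchmarks in Section 1.1 are for Stage IV disease. Section 6.1 keeps screen-failure data at the site, so patients wrongly turned away under item 1 might not be noticed centrally.

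**Working it through.** **Item 1, literal text against evident intent**

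| Patient's MAPK-inhibitor history | Literal result | Evident intent |
|---|---|---|
| None | Barred | May enter |
| Given for unresectable or metastatic disease | Not barred by this item | Barred |
| Given only as adjuvant therapy | Opening words bar; the later adjuvant sentence allows | Not settled by the text |

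The permissive sentences that close the item make sense only if its first sentence was written as an entry requirement. That settles the first two rows. It does not settle the third.

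**Stage, criterion by criterion**

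- The only staging of the study disease in Section 5.2 is inside exclusion 1, where it describes the setting in which earlier therapy was given. It is not an entry condition.
- The T1a wording in exclusion 7 concerns second malignancies. Exclusions 10, 11 and 12g mention metastases only to keep patients out.
- Section 7.5.2 counts a node of at least 15 mm in short axis, or a lesion of at least 10 mm by caliper, ruler or photograph, as measurable. Either can be resectable, and item 4 accepts testing of the primary tumor. Such a patient passes items 3, 4 and 7, and no other item asks about stage.

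**The plan's own figures (Section 13, Table 20)**

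Inputs: 15 patients in stage 1, stop at 0 responses; 25 in total, reject at 4 or more; p0 = 5%, p1 = 25%.

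- Early stopping = (1 − p)^15. At 5%: 0.95^15 = 0.4633 (stated 0.463). At 25%: 0.75^15 = 0.0134 (stated 0.013).
- Rejection = Σ over x = 1 to 15 of P(X = x)·P(Y ≥ 4 − x), with X ~ Bin(15, p) and Y ~ Bin(10, p). At 5%: 0.0336 (stated 0.034). At 25%: 0.9008 (stated 0.901).

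The remaining rows agree to within 0.001, and a minimax search for these error rates returns the same design. The wording faults change none of this.

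**Illustration only**

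The documents do not say how many patients outside the intended population would enter or how they would respond. Suppose a share f of cohort A is outside it and responds at rate q, while the rest respond at 25%. The overall rate is p = 0.25(1 − f) + q·f. With f = 20% and q = 0, p = 0.25 × 0.80 = 0.20, for which Table 20 itself gives 0.762.

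| Share f | p at q = 0 | Power | p at q = 10% | Power |
|---|---|---|---|---|
| 10% | 0.225 | 0.843 | 0.235 | 0.869 |
| 20% | 0.200 | 0.762 | 0.220 | 0.829 |
| 30% | 0.175 | 0.655 | 0.205 | 0.780 |
| 50% | 0.125 | 0.379 | 0.175 | 0.655 |

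This takes one direction. If those patients responded more often than the intended population, the error would run towards a false success instead.

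**The case against.** The strongest reply is that item 1 is a drafting slip with an obvious meaning, and that other parts of the protocol limit the damage.

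- Few otherwise eligible patients are likely to have had a MAPK inhibitor. V600-positive patients are excluded, Section 1.1 says the BRAF and MEK inhibitors are approved only for V600-mutant disease, and Section 1.3.1 calls direct BRAF inhibition apparently ineffective here.
- Registration is central, so there is a second look at each patient.
- Measurable disease is mandatory, so fully resected patients cannot enter.
- Stage at screening is a critical baseline assessment (Section 7.2.1) and metastatic stage is a planned subset factor for progression-free survival (Section 13.3.2.2.2), so patients outside the intended stage would be visible in the data.

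Most of this stands. It makes the inversion alone a minor matter and narrows the stage gap to resectable disease with a measurable lesion. It does not close that gap: recording stage after entry is not an entry rule. Inferring the intent of item 1 also leaves the adjuvant question open, and the protocol forbids departing from the written lists.

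A reader might infer more than the documents support:

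- *That the trial in practice turns away inhibitor-naive patients.* The item's own later sentences point the other way.
- *That a faulty checklist is in use.* The checklist is not among the documents, so its wording is unknown.
- *That the response rate is known to be distorted because one response in 25 is 1/25 = 4 percentage points.* That holds for any misclassified response in this trial and says nothing about how many would occur or in which direction.

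**Conclusion.** Both faults are present in the operative text and should be corrected. Item 1 says the reverse of its evident intent, although most sites would probably read it correctly. The missing advanced-disease criterion is the weightier of the two, because no reading of item 1 supplies it.

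The size of the effect cannot be estimated from the documents. What can be said is that continuation needs 1 response in 15 and success needs 4 in 25, so a few patients from outside the intended population could affect a decision. Under the assumed shares of 10% to 30% and response rates of 0 to 10%, power would lie between 0.655 and 0.869 instead of 0.901. Those inputs are assumptions, not forecasts. The sample size and error rates as stated are sound.

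**What to change.** 1. Reword item 1 so that it begins with *prior therapy* and not *no prior therapy*, or move it to the inclusion list. Separate the permissive sentences from the criterion.
2. State whether a MAPK inhibitor given as adjuvant therapy counts under this item.
3. Add an inclusion criterion that defines advanced disease. The sponsor must first reconcile three descriptions: the garbled stage phrase in exclusion 1, the undefined term *advanced* in Sections 2 and 3.1, and Section 1.1, which describes the licensed use as covering stage IV and unresectable stage III disease. The exclusion 1 phrase should not simply be copied. It describes the setting of earlier therapy, and as an entry rule it could exclude unresectable stage IIIA or IIIB patients. That matters when the high-activity group was 10 of 266 tumors (3.8%) in Section 1.3.2.
4. Bring the eligibility checklist into line with the corrected lists.

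The cost is a few lines in the protocol and checklist, through the usual amendment and review. Whether any intended patient is lost depends on the stage definition chosen in step 3. The design, sample size and analysis are unchanged.

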1.2.3. Clinical Safety of Trametinib

The adverse events (AEs) observed in the pivotal, Phase III registration study (Flaherty 2012) was consistent with that seen across trametinib monotherapy studies and is summarized here. The Phase III study demonstrated that the 2 mg, continuous, once daily dose of trametinib has an acceptable safety profile. Adverse events occurring in $\geq 15\%$ of subjects that received at least one dose of trametinib (N=211) were rash (57%), diarrhea (43%), peripheral edema (26%), fatigue (26%), dermatitis acneiform (19%), nausea (18%), alopecia (17%), and hypertension (15%). Less than 8% of the subjects had grade 3 or 4 rash (including only one patient with grade 4), and no grade 3 or 4 diarrhea was observed. Decreased ejection fraction or ventricular dysfunction occurred in 7% of the subjects, and $<1\%$ (n=2) had grade 3 cardiac-related events that were considered trametinib related and led to permanent discontinuation of the study treatment. Ocular events, most of which were grade 1 or 2, occurred in 9% of the subjects. Blurred vision was the most frequent ocular event (4%), and there was one case of reversible chorioretinopathy. Retinal vein occlusion, an AE that has been associated with MEK inhibitors, was observed only extremely rarely. Rash, diarrhea, visual disorders, hepatic disorders, cardiac-related AEs, and pneumonitis are considered AEs of special interest for trametinib because they are either known class effects (i.e. were observed with other MEK inhibitors) or are potentially life-threatening.

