Appendix 2 : NYHA Functional Classification System

The **New York Heart Association (NYHA) Functional Classification: Class I, II, III or IV Heart Failure** [NYHA, 1994] provides a simple way of classifying the extent of heart failure. It places subjects in one of 4 categories based on the level of limitation experienced during physical activity:

Class	Symptoms
Class I (Mild)	No limitation of physical activity. Ordinary physical activity does not cause undue fatigue, palpitation or dyspnea (shortness of breath).
Class II (Mild)	Slight limitation of physical activity. Comfortable at rest, but ordinary physical activity results in fatigue, palpitation or dyspnea.
Class III (Moderate)	Marked limitation of physical activity. Comfortable at rest, but less than ordinary physical activity results in fatigue, palpitation or dyspnea.
Class IV (Severe)	Unable to carry out any physical activity without discomfort. Symptoms of cardiac insufficiency at rest. If any physical activity is undertaken, discomfort is increased.

Reference:

The Criteria Committee of the New York Heart Association (NYHA). Nomenclature and Criteria for Diagnosis of Diseases of the Heart and Great Vessels. 9th Ed. Boston, Mass: Little, Brown & Co.; 1994:253-256.

CONFIDENTIAL

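### Exclusion 12d names only NYHA Class I heart failure, the least limited class in Appendix 2, and no eligibility criterion names Classes II to IV

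*Combined protocol and SAP*

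**What the plan says.** Item 12 of section 5.2.2 (Exclusion Criteria) lists cardiovascular exclusions. Sub-item d reads "A history or evidence of current Class I congestive heart failure", and refers to the NYHA guidelines in Appendix 2 for the definition.

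Appendix 2 introduces the scale: "It places subjects in one of 4 categories based on the level of limitation experienced during physical activity". Its four descriptions begin as follows:

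- Class I: "No limitation of physical activity"
- Class II: "Slight limitation of physical activity"
- Class III: "Marked limitation of physical activity"
- Class IV: "Unable to carry out any physical activity without discomfort"

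Section 5.2.2 also says that departures from the exclusion criteria are not permitted and that they must be followed as specified. Section 3.1 rules out waivers and requires an eligibility checklist in each enrollment packet.

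On why cardiac status matters for this drug, section 1.2.3 reports from the phase III study: "Decreased ejection fraction or ventricular dysfunction occurred in 7% of the subjects".

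**The concern.** A heart-failure exclusion tied to a graded scale would be expected to name a grade and say whether it reaches upward. 12d names the bottom grade and stops. Taken by itself, it turns away a patient whose heart failure causes no limitation and says nothing about a patient who is limited by it.

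Two things are at stake. The first is safety screening. The protocol counts cardiac events among the adverse events of special interest for trametinib, and sites that may not depart from the text are given a cardiac criterion whose literal meaning is at odds with its own reference. The second is consistency. Several sites enroll, and the wording can pass into the checklist that each of them completes. If some sites read 12d literally and others read it as Class I and above, the enrolled population differs by site. It could also complicate safety assessment: Table 4 in section 3.9.1.1 separates asymptomatic from symptomatic LVEF decline and lists dyspnea among the symptoms, while Appendix 2 gives dyspnea on ordinary activity as a Class II feature. A patient who enters with that symptom is harder to place in that table later.

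**Working it through.** No formula applies, and the plan states no figure on this point. The check sets the criterion beside its scale and then beside every other criterion that might do the same job.

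**Step 1: 12d against Appendix 2.**

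| NYHA class | Limitation described in Appendix 2 | Named in 12d | Named in any other criterion (5.2.1, 5.2.2, Table 13) |
|---|---|---|---|
| I | None | Yes | No |
| II | Slight | No | No |
| III | Marked | No | No |
| IV | No activity without discomfort; symptoms at rest | No | No |

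One class of 4 is named; 4 − 1 = 3 are named nowhere in the eligibility criteria. Appendix 2 attaches the label *Mild* to both Class I and Class II, so the ordering rests on the descriptions rather than the labels. No limitation is plainly less than slight limitation, so Class I is the least severe.

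**Step 2: could a symbol have been lost?** The text was read from PDF by a program, so a missing sign before *Class I* cannot be ruled out. Against that, comparison signs survive in the same list: at least 480 msec in 12a, more than 30 days in 12b, the blood-pressure limits in 12e and the intraocular-pressure limit in 13b. Loss is possible but is not the evident explanation.

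**Step 3: what else would catch Classes II to IV?**

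- *Table 13, LVEF at or above LLN* (above 50% if no LLN is specified). This removes heart failure with an ejection fraction below the limit, whatever the class. It is an imaging threshold and does not see symptoms when the ejection fraction is at or above LLN.
- *Inclusion 12, ECOG 0 or 1.* Appendix 4 allows ECOG 1 for a patient restricted in strenuous exertion who walks about and can do light work. That is hard to square with Class IV and constrains Class III in part. It overlaps with the slight limitation of Class II and does not reliably remove it.
- *Exclusion 8, serious or unstable pre-existing conditions.* This is mandatory, but it names neither heart failure nor an NYHA class, and it calls for a judgement on the individual patient.
- *The opening of item 12.* It refers to cardiovascular risk in general and introduces the sub-items with the word *including*, which can be read as non-exhaustive. A site may equally reason that a sub-item naming one class leaves the others outside it.

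**Step 4: what remains.** The two objective filters, LVEF and ECOG, leave mainly Class II, and perhaps some Class III, with LVEF at or above LLN. For those patients the outcome depends on how a site reads exclusion 8 and the opening of item 12.

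**The case against.** The strongest reply is that eligibility is decided by the whole list, not by one sub-item. A patient with symptoms at rest is unlikely to be ECOG 0 or 1. A patient with reduced ejection fraction fails Table 13. The instruction to apply the criteria as written binds sites to exclusion 8 and to the opening of item 12 as firmly as to 12d. LVEF is also monitored on treatment and has its own stopping criteria in section 3.9.1.1. Most of this stands, and it narrows the point considerably.

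It also defeats two stronger readings. A reader might infer that the protocol makes Class II to IV patients eligible, or that its cardiac screening as a whole runs backwards. The documents do not support that: those classes are unnamed, which is not the same as admitted, and four other provisions bear on them. A reader might also size the problem from the 7% in section 1.2.3, as 0.07 × 25 = 1.75 patients in a full cohort. That figure is an on-treatment event rate from a phase III study in BRAF V600-mutant melanoma. It does not count patients who present with Class II to IV heart failure and pass the other criteria, and those events could occur whatever 12d says. The base is incomplete too, since 12d applies to both cohorts, up to 25 + 25 = 50 patients.

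What the reply does not remove is the conflict itself. A specific criterion should not need general clauses to offset its literal meaning, and the patients left after the objective filters depend on judgement.

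**Conclusion.** The point holds in a limited form. As written, 12d names one of the four classes in Appendix 2, and that class is the least limited; the other three appear in no eligibility criterion. This is an error in a stated rule rather than a missing detail. Its practical reach is mainly symptomatic heart failure with LVEF at or above LLN, in Class II and perhaps some Class III.

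The number of patients affected is unknown. The documents give no figure for it, and it may be small. The primary response-rate analysis, its error rates and the two-stage stopping rule are untouched.

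The conclusion assumes that the text of 12d is as the sponsor wrote it. If the source document carries a sign or an *or higher* that was lost in reading, the point falls away. It takes no position on which classes ought to be excluded.

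**What to change.** 1. Check 12d against the source document to settle whether a character was lost.
2. If the wording is as shown, reconcile 12d with Appendix 2 and state explicitly which NYHA class or classes the sponsor means to exclude. That choice is the sponsor's.
3. Carry the same wording to the eligibility checklist, so that all sites apply one rule.

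The cost is one line in the protocol and one in the checklist, with the usual amendment approval. No sample size, analysis or assessment schedule changes.
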